4. BMI
5. SBP
6. DBP
7. HR
8. AF duration
9. LVEF
10. Diabetes
11. Current Smoking
12. Hypertension
13. Hypercholesterolaemia
14. Previous MI
15. Previous PCI

Demographic and baseline data will be summarised by randomisation group and overall. For continuous data the number of subjects, mean, SD, median and interquartile range will be shown. For categorical data number and percentage will be shown. No formal testing will be performed for the comparison of baseline characteristics.

10 Interim analysis and timing for analysis.

10.1 Interim analysis

On completion of the 6-week blinding period of the last patient to be enrolled into the pilot study, an interim analysis will be performed, including endpoints assessed from baseline to 6-weeks. No other interim analyses are planned prior to the completion of the study, unless specifically requested by the DSMC.

The main analysis will take place at the end of this pilot study and this information will be used to inform decisions regarding procedure to a main future trial. Patients will be followed up for 12 months regardless of interim analysis results.

10.2 Time points for analysis.

The DSMC will monitor patient safety and will meet prior to initiation of the study, after the recruitment of 4 patients and then at 3 monthly intervals. All other analysis described in this SAP will take place at the end of this pilot study.

11 Feasibility and Efficacy Analysis

11.1 Method for analysis of endpoints

11.1.1 Analysis of feasibility endpoints

Proportions will be shown along with the number with each binary endpoint and total number.

The recruitment rate will be shown overall as the total number of patients recruited divided by the number of months.

Data completeness will be assessed as the numbers with and without data recorded and the proportion with complete data for each treatment group and overall.

For the blinding index, the number and percentage with each response will be given for each treatment arm. The blinding index will be reported for each group.

Other feasibility endpoints, including assessment of key study logistics, and the feasibility of blinding SOP, acceptability of interventions, will be assessed more qualitatively, and hence will not be described further in this SAP.

11.1.2 Analysis of efficacy endpoints

Categorical variables will be shown as the number with each endpoint and total number in each group along with the proportion. Odds ratios and 80% one-sided exact confidence intervals will also be shown as an assessment of efficacy, an approach described by Cocks et al⁴.

For continuous variables mean, SD, and number of patients with available data will be presented along with estimated mean difference between trial arms and 80% one-sided confidence intervals.

For AF burden (proportion of time in AF), median and IQR will also be reported.

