6.2 Secondary objective

The secondary objective of the trial will be to determine whether an early-ablation strategy is superior in terms of patient's quality of life than a cardioversion strategy, and to compare medication burden, cost efficacy and secondary endpoints of cardiac function (change in ejection fraction) between these strategies. Finally, the safety of the approaches will be compared.

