6.4.5 Assessment of primary and secondary efficacy endpoints

The primary endpoint is defined as the proportion of randomised patients with recurrent AF (AF episode lasting > 7 days) within 12 months, but outside of the initial 6-week blanking period (see section 8.1.2).

Secondary endpoints to be described are:

- Proportion dying within 12 months
- Proportion with hospital admission for any reason within 12 months
- Proportion with procedural-related complications defined as any AE that is deemed at least possibly related to intervention
- Proportion with bleeding events within 7 days of procedure
- Proportion with repeat procedures (any additional procedure for AF after the baseline index trial procedure(s)) within 12 months
- Change in ejection fraction from baseline at 12 months
- Proportion with clinical success of procedure
- Change in QoL at 12 months, as measured by SF-12 and AF-PROMS
- AF burden by 12 months
- Anti-arrhythmic drug use.

Clinical success will be defined as a 75% or greater reduction in the number of AF episodes as measured by the Reveal LINQ implant device within 12 months, but outside of the initial 6-week blanking period.

Change in QOL will be measured by the change in AF-PROMS summary scores and SF-12 PCS and MCS between screening and 12 months. SF-12 scores will be calculated as described in the appendix supplementary table 2³.

AF burden will be defined as the proportion of time in AF over the 12 months but outside of the initial 6-week blanking period, as measured by the Reveal LINQ implant device.

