6.5 Level of significance

No hypothesis testing will be done for this pilot study.

For efficacy outcome measures we will use 80% one-sided confidence intervals to give an indication of whether the endpoint is likely to be of interest, an approach described by Cocks et al. for pilot trials⁴.

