12.1 Adverse events (AE)

AEs will be summarised using counts and percentages. The number of subjects having at least one AE will be presented overall and tabulated by treatment. The number of subjects with AEs of mild/moderate/severe intensity will be shown overall and by treatment using the maximum severity experienced for each patient. The total number of AEs for each treatment, allowing multiple events per patient, will also be presented.

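### The one-sided 80% odds-ratio limit planned for death, procedural complications and bleeding puts no ceiling on harm at 10 per arm, and no other planned output does

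*SAP*

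**What the plan says.** Protocol 6.2 ends its secondary objectives with a safety comparison: "Finally, the safety of the approaches will be compared".

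SAP 6.4.2 and 6.4.5 list death within 12 months, bleeding within 7 days and procedural complications among the secondary efficacy endpoints. Complications are defined broadly: "Proportion with procedural-related complications defined as any AE that is deemed at least possibly related to intervention". Table 4, the efficacy table for the ITT population, has a row for each of the three and a column for the odds ratio with an 80% interval.

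SAP 11.1.2 sets the method: "Categorical variables will be shown as the number with each endpoint and total number in each group along with the proportion", and then "Odds ratios and 80% one-sided exact confidence intervals will also be shown as an assessment of efficacy". SAP 6.5 gives the purpose of the limit, which is "to give an indication of whether the endpoint is likely to be of interest", and also states that "No hypothesis testing will be done for this pilot study".

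For safety proper, SAP 12.1 says "AEs will be summarised using counts and percentages". Table 5 follows that, and Table 6 lists SAEs. Neither has an interval or a between-arm measure. The SAP does not say whether the one-sided limit is the lower or the upper one, or how a table with a zero cell is handled.

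**The concern.** A one-sided limit used to judge whether an efficacy endpoint is of interest answers a different question from the one a reader has about harm. For harm the useful question is how large the risk could still be, given what was seen. With ten patients per arm and uncommon events, the odds ratio is a poor vehicle for that: it does not exist when neither arm has an event, and it has no finite upper limit when the control arm has none.

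At stake is the reporting of the safety comparison that Protocol 6.2 promises. Three harm rows could show a blank, an infinite limit or a lower limit, and nothing else in the report would state how much risk the pilot leaves open. SAP 10.1 says the end-of-pilot analysis will inform the decision on a main trial, so the harm rows should say plainly what ten patients per arm can and cannot exclude.

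**Working it through.** **Inputs**
- 10 patients per arm (Protocol synopsis). SAP 6.6 describes the pilot as around 10% of the main trial; 10% of 208 is 20.8, consistent with 20. The plan states no operating figure for the 80% limit, so there is none to reproduce.
- Procedural death with ablation below 0.1% (Protocol 10.1.2). Twelve-month all-cause death is not given.
- Groin bleeding or bruising with ablation 5% (Protocol 10.1.2). Added groin-access risk in the placebo arm below 0.2% (Protocol 10.1.3).
- DCCV skin or chest events 5% and sedation complications below 1% (Protocol 10.1.1). Both arms receive DCCV and groin sheaths.
- Assumed control risk for the broad complications endpoint: 5% + 1% + 0.2% = 6.2%, or 11.2% if 5% bruising is added.

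The odds ratio is taken as PVI relative to DCCV.

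**If the lower limit is reported.** The exact conditional lower limit ψ puts 20% in the upper tail.
- 1 v 0 events: ψ/(1+ψ) = 0.20, so ψ = 0.25.
- 2 v 0 events: 45ψ²/(45ψ² + 100ψ + 45) = 0.20, so 36ψ² − 20ψ − 9 = 0 and ψ = 0.85.
- 3 v 0 events: ψ = 1.61.

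These are finite, but they bound the odds ratio from below only. None says how large the harm could be.

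**If the upper limit is reported.** With no DCCV event it is infinite if PVI has an event, and undefined if PVI has none. The probability is (1 − control risk)^10.

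| Control risk | Calculation | Infinite or undefined |
|---|---|---|
| 0.2% | 0.998^10 | 98% |
| 5% | 0.95^10 | 60% |
| 6.2% (assumed, complications) | 0.938^10 | 53% |
| 11.2% (assumed, complications) | 0.888^10 | 30% |

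**If neither arm has an event** there is no odds ratio. For death at a common risk p the probability is (1 − p)^20: 98% at 0.1%, 82% at 1% and 67% at 2%. The last two rates are assumptions that show the range, because 12-month mortality is not stated.

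**What can be reported in every case**
- Exact (Clopper-Pearson) one-sided 95% upper limit for one arm's risk. For 0/10 it is 1 − 0.05^(1/10) = 25.9%. For 1/10 it is 39.4% and for 2/10 it is 50.7%.
- Newcombe 95% interval for the PVI-minus-DCCV risk difference, built from the Wilson limits. For 0/10 these are 0 and 27.8%; for 2/10 they are 5.7% and 51.0%.
  - 0 v 0: 0 ± 0.278, or −28 to +28 percentage points.
  - 2 v 0: lower 0.20 − √[(0.200 − 0.057)² + 0.278²] = −0.11; upper 0.20 + (0.510 − 0.200) = 0.51. That is −11 to +51 points.

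**The case against.** A reader might infer that the SAP treats any limit including 1 as showing no safety concern, so that 2 v 0 complications would be dismissed and large harms missed at a calculable rate. The documents do not support that. SAP 6.5 rules out hypothesis testing and calls the limit only an indication; it names no threshold and prescribes no reading for harm. Missed-harm rates would describe a rule the plan does not contain.

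It is also true that low detection comes from the sample size. At true risks of 20% v 5%, the lower 80% odds-ratio limit lies above 1 in 23% of trials, whereas the 95% Newcombe interval excludes zero in 7%. The fix therefore flags harm less often, and must be justified on other grounds.

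Nor is every row affected. The 0.2% figure is only added groin-access risk and does not describe the broad complications endpoint, where DCCV events alone give the control arm a material rate. The documents do not show that the other Table 4 outcomes are sparse.

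Finally, safety is covered elsewhere. Counts per arm stand beside the odds ratio, AEs and SAEs are tabulated and listed, and the DSMC sees unblinded data after four patients and then every three months (Protocol 19; SAP 10.2). The progression criteria in Protocol 11.2 are operational, and none is an odds ratio for harm.

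All of this limits the point. It does not supply a bound on risk in the report. A reader could compute one from n/N, but the plan neither provides nor prespecifies it.

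**Conclusion.** The point holds as one of measure and presentation, of minor to moderate severity. For the three harm endpoints the plan prespecifies a statistic whose direction is unstated and which bounds harm in neither direction when events are sparse.

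This is most secure for death (no odds ratio in about 98% of trials at 0.1% per arm, 67% at 2%). For bleeding the upper limit is infinite or undefined in 60% to 98% at control risks of 5% to 0.2%. For complications the share is roughly 30% to 53% and depends on assumed control risks of 11.2% to 6.2%. The calculations assume 10 patients analysed per arm and, for bleeding and death, that the protocol's procedural risks apply. They do not show that the pilot would declare PVI safe, or that progression would turn on these rows.

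**What to change.** - In SAP 6.4, 11.1.2 and Table 4, take death, procedural-related complications and bleeding out of the efficacy odds-ratio analysis and place them in SAP section 12.
- For each, report n/N per arm, the exact one-sided 95% upper limit of each arm's risk, and the PVI-minus-DCCV risk difference with a 95% Newcombe or score interval.
- State the analysis population for these rows. Table 4 uses all randomised patients, while SAP 7.2.2 limits the safety population to those who received their allocated treatment, so the move would otherwise change the denominators.
- Add a sentence that an interval including no difference is not evidence of similar safety.
- For the endpoints that keep the odds ratio, state which one-sided limit is reported and how zero cells are handled.

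The cost is SAP wording and three table rows, with no new data. The downside is that the intervals will be wide and less reassuring.

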11.1.3 Analysis of subgroups

There is no plan to conduct any subgroup analyses.

11.1.4 Covariate adjusted analysis

No covariate adjustment will take place.

11.2 Assumptions for analysis.

For continuous efficacy outcomes, confidence intervals for differences will be constructed assuming a normal distribution. Normality of distribution for continuous variables is hard to assess with such a small number of subjects in this pilot trial and so will not have much value.

11.3 Methods for handling of missing data and outliers

This pilot study will assess data completeness to inform decisions about missing data for a future main trial. Analysis will use all patients with available endpoint data. The level of missing data will be tabulated for each outcome, presenting the number of subjects with a data record and number with missing data, separately by trial arm.

11.4 Multiple comparisons

No adjustment for multiple comparisons will be made.

11.5 Multi-centre studies

No adjustment will be made for centre in this pilot study.

12 Safety analysis

12.1 Adverse events (AE)

AEs will be summarised using counts and percentages. The number of subjects having at least one AE will be presented overall and tabulated by treatment. The number of subjects with AEs of mild/moderate/severe intensity will be shown overall and by treatment using the maximum severity experienced for each patient. The total number of AEs for each treatment, allowing multiple events per patient, will also be presented.

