9.10 Subject Withdrawal

Patients can withdraw from the trial at any time and without giving a reason. The Principal Investigator can also withdraw a patient from the study for any of the following reasons:

1. Any adverse event or serious adverse event
2. Any concurrent illness that prevents further treatment
3. Any change in the patient's condition that justifies the discontinuation of treatment in the clinician's opinion
4. Withdrawal of consent for treatment by the patient
5. Any study device or procedural complications
6. Any reasons the subject cannot adhere to study visits or procedures

If a patient withdraws from the study, another patient will be randomised to replace them. Patients who are randomised but withdraw will not have their medical care affected and return to standard clinical care.

10. Assessment and management of risk

The risks of both DC cardioversion and of catheter ablation for AF are well established, as detailed below. However, the procedures will be performed by experienced clinicians who part of the research team for all study participants, which should minimise any known/expected risks.

10.1.1 DCCV risks:

- Sedation complications (<1%), chest discomfort, redness, irritation at site of skin pads (5%), failure of DCCV.

10.1.2 Catheter ablation of AF risks:

- Groin access complications (1% historically, <0.2% with ultrasound guidance)
- Minor (Total <6%)
 - Groin: Bleeding bruising at groin access site (5%)
 - Pericardial effusion not requiring drainage (1%)
 - Transient phrenic nerve palsy (3%)
- Major (Total <1%)
 - Groin complication or vascular damage requiring surgical or radiological intervention (0.5%)
 - Cardiac tamponade requiring percutaneous drainage (0.7%)
 - Stroke (<0.2%)
 - Oesophageal damage (<0.2%)
 - Death (<0.1%)
 - Pulmonary vein stenosis causing breathlessness (<0.1%)

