17.3 Notification and reporting of Adverse Events and Reactions

If the AE is not defined as serious, the AE will be recorded in the study documents and the participant followed up by the research team. The AE will be documented in the participants' source documents, the Case Report Form (CRF), and, where appropriate, medical records.

The following events will be considered and reported as Adverse Events, and not serious adverse events, as they are expected as known complications of procedures:

- Phrenic nerve damage
- Tamponade or pericardial effusion
- Haematoma
- Skin Burns
- Chest pain
- Groin vascular complications.

The period for adverse events reporting will be from the signing of consent until the end of study visit at 12 month follow-up.

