17.4 Serious Adverse Events (SAEs) or reactions

A serious adverse event (SAE) is defined as an untoward occurrence that:

- Results in death,
- Is life-threatening,
- Requires hospitalisation or prolongation of existing hospitalisation,
- Results in persistent or significant disability or incapacity,
- Consists of a congenital anomaly or birth defect, or
- Is otherwise considered medically significant by the investigator.

SARs will be reported to the REC where in the opinion of the Chief Investigator the event was serious and:

- Related (it may have resulted from administration of any of the research interventions), and
- Unexpected (the type of event is not listed in the protocol or other Reference Safety Information as an expected occurrence).

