13	Safety analysis.....	16
13.1	Adverse events (AE)	16
13.2	Deaths or serious adverse events (SAE)	16
14	Presentation of analysis	17
15	REFERENCES	23

4 GLOSSARY of Terms and Abbreviations

AE	Adverse event
AF	Atrial Fibrillation
BMI	Body Mass Index
BP	Blood Pressure
CHADS	Score for estimating AF stroke risk
CI	Confidence Interval
DBP	Diastolic Blood Pressure
DC	Direct Current
DCCV	Direct Current Cardioversion
DSMC	Data and Safety Monitoring Committee
ECG	Electrocardiogram
FU	Follow-up
HR	Heart Rate
IQR	Interquartile Range
LA	Left Atrial
LINQ	Reveal LINQ cardiac monitoring system
LVEF	Left Ventricular Ejection Fraction
MCS	Mental Health Composite Scale (SF-12)
MI	Myocardial infarction
BI	Blinding Index
OR	Odds Ratio
PCI	Percutaneous Coronary Intervention
PCS	Physical Health Composite Scale (SF-12)
PROMS	Patient Reported Outcome Measures
PVI	Pulmonary Vein Isolation
QoL	Quality of Life
R	“R” Statistical Programming Software
SAE	Serious Adverse Event
SAP	Statistical Analysis Plan
SF-12	Twelve item short form survey
SBP	Systolic Blood Pressure
SD	Standard Deviation

5 Introduction

This SAP has been written based on information from the study protocol version 2.0, dated 25/06/2019.

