7.2.2 Safety population

The safety population will consist of all randomised patients who received the allocated treatment.

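### Procedural harms that Protocol 17.3 classes as AEs and not SAEs appear by arm only in pooled rows; the one SAP output with event terms, Table 6, lists SAEs only

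*SAP*

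**What the plan says.** SAP 12.1 states that "The number of subjects having at least one AE will be presented overall and tabulated by treatment". It adds the number of patients by worst severity and the total number of AEs per arm. Table 5 has exactly those rows and no row by event type. Under SAP 12.2, SAEs are listed individually, and Table 6 gives each a coded term, the arm, relatedness and whether it was expected. No other output carries an event term.

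Table 4 has two further rows that these events can enter: procedural-related complications, which SAP 6.4.5 defines as any AE at least possibly related to the intervention, and bleeding within 7 days.

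Protocol 17.3 says "The following events will be considered and reported as Adverse Events, and not serious adverse events", and gives as the reason that they are known complications. The list includes "Tamponade or pericardial effusion", along with phrenic nerve damage, groin vascular complications, haematoma, skin burns and chest pain.

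Protocol 17.4 begins "A serious adverse event (SAE) is defined as an untoward occurrence that" and then gives criteria based on outcome, among them "Requires hospitalisation or prolongation of existing hospitalisation". It makes no exception for the events in 17.3.

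On populations, SAP 7.2.2 says "The safety population will consist of all randomised patients who received the allocated treatment". Table 4 uses the intention-to-treat population and Table 5 the safety population.

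**The concern.** Protocol 6.2 undertakes to compare the safety of the two approaches. Phrenic palsy and tamponade are mainly harms of the ablation arm. Groin injury can occur in both arms, because the DCCV-only patients also receive femoral sheaths, and Protocol 10.1.3 gives groin access as the risk added for them. If one of these events occurs, the planned tables show that a patient had an AE of some severity, or a related complication, but not which one. A pad-site skin reaction and a pericardial effusion enter the same counts, separated at most by severity grade. If 17.3 is applied as written, a tamponade needing drainage could also be missing from the SAE listing in the arm where it is most likely.

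The choice of population adds a second gap. If a complication at transseptal puncture stops the ablation, that patient has not received the allocated treatment and leaves Table 5.

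**Working it through.** The plan states no figure on this point, so the check is mainly textual, followed by a calculation of scale.

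**1. Where each event goes.**

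| Event | If 17.3 overrides 17.4 | If 17.4 overrides 17.3 |
|---|---|---|
| Transient phrenic palsy, not serious | Pooled rows only | Pooled rows only |
| Undrained effusion, not serious | Pooled rows only | Pooled rows only |
| Tamponade meeting a 17.4 criterion | Pooled rows only | Pooled rows, and named in Table 6 |
| Groin injury meeting a 17.4 criterion | Pooled rows only | Pooled rows, and named in Table 6 |

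The pooled rows are procedural-related complications in Table 4 and any AE, maximum severity and total AEs in Table 5. A groin bleed within 7 days also enters the bleeding row. The first two lines of the table do not depend on how the conflict between 17.3 and 17.4 is settled.

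**2. Who is counted.** A patient whose ablation is stopped by a complication is outside the SAP 7.2.2 population, and so outside Table 5. That patient is still randomised and stays in the pooled Table 4 row. Protocol 9.10 also lets the investigator withdraw a patient for "Any study device or procedural complications", and a withdrawn patient is replaced.

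**3. Inputs for scale.** The synopsis gives 10 patients per group. Protocol 10.1.2 gives transient phrenic palsy 3%, undrained effusion 1%, tamponade needing drainage 0.7%, and groin or vascular injury needing intervention 0.5%.

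These item rates do not agree with the Protocol's own totals:

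- Minor: 5 + 1 + 3 = 9%, against a stated total below 6%.
- Major: 0.5 + 0.7 = 1.2% from the two firm items, against a stated total below 1%. With the four items given only as limits set at those limits, 1.2 + 0.2 + 0.2 + 0.1 + 0.1 = 1.8%.

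**4. Chance of at least one event in 10 ablated patients**, 1 - (1 - p)^10, assuming independence between patients and between event types:

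- Phrenic palsy: 1 - 0.97^10 = 26.3%.
- Phrenic palsy or undrained effusion: 1 - (0.97 × 0.99)^10 = 33.3%.
- Tamponade: 1 - 0.993^10 = 6.8%.
- Major groin injury: 1 - 0.995^10 = 4.9%.
- Any of the four: 1 - (0.97 × 0.99 × 0.993 × 0.995)^10 = 40.9%. With the two major items together held to 1%: 1 - (0.97 × 0.99 × 0.99)^10 = 39.7%.

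The 5% groin bleeding or bruising item is left out because it is largely covered by the bleeding row. Groin events in the DCCV-only arm are not counted either.

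**5. What a zero would show.** With 0 events in 10 patients, the one-sided 95% upper limit is 1 - 0.05^(1/10) = 25.9%.

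**The case against.** **The reading of 17.3.** The list in 17.3 follows a sentence about AEs that are not serious, and 17.4 defines seriousness by outcome without exception. Table 6 also records whether each SAE was expected, so the SAP foresees that expected SAEs will be listed. On that reading a life-threatening tamponade appears in Table 6 by term and arm. This objection has real force. A reader might infer that the plan certainly hides tamponade from the SAE listing, and the documents do not support that. What they do show is two clauses that conflict and a listing whose content depends on which one a site follows. The non-serious events are unaffected by the objection.

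**The version.** The SAP says "This SAP has been written based on information from the study protocol version 2.0, dated 25/06/2019", while the supplied protocol carries signatures dated 12 February 2019. The version 2.0 wording of 17.3 cannot be confirmed from these documents. This limit stands.

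**The totals as a ceiling.** A reader might infer that the Protocol's totals cap the chances in the working. Shrinking every minor item by 6/9, for example, puts phrenic palsy at 2%, which gives 1 - 0.98^10 = 18%. Nothing in the Protocol says the items shrink in proportion. Phrenic palsy at 3% plus effusion at 1% is 4%, already under the 6% total, and tamponade at 0.7% is under the 1% total. Neither 18% nor the item-rate figures are upper limits.

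**Consequence.** This is a 20-patient pilot with operational aims and no hypothesis testing. The events are recorded in the CRF, the DSMC has unblinded data, and complication rates are not a progression criterion. Neither document promises a breakdown by event type. All of this is correct, and it keeps the point minor. It does not remove it, because a stated classification rule can leave the SAE listing short in one arm.

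**Conclusion.** The point holds as a gap in safety reporting that could usefully be closed. Under any reading of the supplied text, non-serious phrenic palsy and undrained effusion are counted by arm but never named. For tamponade and groin injury that meet a 17.4 criterion, omission from Table 6 is conditional on 17.3 prevailing, and on version 2.0 keeping the same wording. A patient whose ablation is stopped by a complication leaves Table 5 but remains in Table 4, so the event is not lost altogether; what is lost is its identity.

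The scale is about a one-in-four chance that the pilot sees a phrenic palsy, one in three for phrenic palsy or undrained effusion, 7% for tamponade and 5% for major groin injury. These rest on the Protocol's own item rates, 10 ablated patients and independence, and are illustrative because the item rates exceed the Protocol's totals. No efficacy estimate is biased and no progression decision changes.

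**What to change.** Extend the Table 6 listing, by term and arm, to every event named in Protocol 17.3 and every AE at least possibly related to the procedure. Add a column stating whether the event meets the 17.4 seriousness criteria, so that the listing no longer depends on which clause a site follows.

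Add three descriptive rows giving n/N by arm, without odds ratios: phrenic nerve damage; tamponade or effusion; groin vascular complications. Count them in all randomised patients, including anyone withdrawn and replaced under Protocol 9.10. Leave the existing rows of Tables 4 and 5 as they are.

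The cost is SAP wording, one longer listing and three rows, from data already held in the source documents and CRF. The output will be slightly longer and contain many zeros, and 10 patients per arm cannot support an estimate of any rate.
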